After passing an initial prescreening, potential participants will provide informed consent and be administered emailed, phone or videoconference-based screening assessments by trained research staff to assess the above inclusion and exclusion criteria. Participants who qualify after completing all screening assessments will then be sent or provided the study materials. This consists of study medication and self-monitoring equipment, including, as needed, a pregnancy test [for females of childbearing age not using contraception], oxygen saturation monitor, automated blood pressure monitor, and thermometer. We will finalize screening (ie confirming medical stability via oxygen saturation monitor, and vital sign measurement) prior to instructing participants to begin taking study medication, after which point (after taking first dose) they are considered "randomized", consistent with Intention to Treat principles.

Study Design

This study will randomize approximately n=152 participants. This study has an initial double-blind phase (to test the drug's effectiveness) followed by an open-label phase (to provide all participants with exposure to the drug, and allow a taper off of it for those initially taking active drug).

Assignment will be 1:1; (1) Active treatment: start and maintain fluvoxamine 100mg, three times daily. May reduce dose (or start at reduced dose) for tolerability reasons; (2) Control: placebo, three times daily. This drug vs placebo phase will last approximately 15 days and will be followed by an open-label fluvoxamine phase that will typically last 6-7 days but could last up to 15 days: 100mg two times daily for 3 days, then 50mg two times daily for 3 days, then discontinue.

Randomization will be stratified by age (we anticipate: 18-44, 45-54, 55-64 and ≥ 65 years, respectively, to reflect the age distribution of ascending risk for severe symptoms requiring hospitalization (https://www.cdc.gov/mmwr/volumes/69/wr/mm6912e2.htm#F2_down) and sex. Final determination of stratification will be made by the biostatistician ([name]). Stratified randomization schedules will be generated by statistician [name].

After the randomized phase, all participants will be followed for approximately 30 days to collect clinical data (i.e., on hospitalization and other clinical outcomes). Thus, total study participation is approximately 45 days (15 days randomized, 30 days follow-up).

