Definition of clinical worsening: Clinical worsening is defined meeting both of the following: (1) presence of dyspnea and/or hospitalization for shortness of breath or pneumonia, plus (2) decrease in O₂ saturation ($<92\%$) on room air and/or supplemental oxygen requirement in order to keep O₂ saturation $>92\%$. A laboratory-confirmed clinical endpoint is consistent with World Health Organization clinical trial recommendations (<https://www.who.int/blueprint/15-01-2020-nfr-bp-wg-clinical-trials-ncov.pdf?ua=1>).

Power analysis: The below table regards the primary endpoint. It assumes 80% power, alpha=0.05, and a 20% rate of progression to serious symptoms in the placebo group. The table shows sample size required based on reduction in that rate in the active (fluvoxamine) group. With total n=152 (76 per group), we would have 80% power to find a statistically significant difference in survival curves (i.e., time to clinical worsening) if the rate of progression with fluvoxamine is only 5% (i.e., a three-quarters reduction in the risk of clinical deterioration). This power calculation is conservative because it does not take into account the potentially improved power gained by stratification, or the enhanced power for Kaplan Meier vs. simple rates; therefore, we are likely to be sufficiently powered for a more modest treatment effect.

Treatment Response	N (each group)
.05	76
.06	90
.07	108
.08	131
.09	160
.10	199

We will also examine the following secondary endpoints:

1. clinical deterioration on a Likert-type scale: (1) moderate severity of illness as defined by O2 saturation <92% but no supplemental oxygen requirement; (2) O2 saturation plus supplemental oxygen requirement; (3) O2 saturation <92% plus hospitalization (related to dyspnea/hypoxia); (4) the above, plus ventilator support requirement; (5) the above, plus ventilator support for at least 3 days; (6) death.

2. clinical deterioration measured by number of days: (1) requiring supplemental oxygen; (2) requiring hospitalization; (3) requiring ventilator support.

These Likert-type assessments are based on our review of current COVID-19 treatment studies.

They will be collected in retrospect via patient or family report and/or medical records.

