3. Total symptomatic severity during the 15 days using a continuous scale of each patient's presenting symptoms on a 0-10 Likert scale (0= symptom not present, 10= symptom is very severe). Outcomes will be collected daily, with symptomatic data collected approximately twice daily via the technique of Ecological Momentary Assessment (ie "how bad is your symptom right now?"). The most severe symptom at baseline will be the focus. This data collection and analytic technique (with frequent measurement of the symptom[s] most relevant to the individual patient) should greatly increase precision and power (<https://www.ncbi.nlm.nih.gov/pmc/articles/PMC6524455/>).

Data management and analysis: Data will be collected in REDCap and outcomes will be collected by blinded research staff. The study statistician, [name], will conduct blinded (ie "treatment 1 vs treatment 2") analysis under the supervision of [name]. We may conduct an interim "futility" analysis at approximately n=100 participants. The primary analysis will be survival analysis of the primary outcome (clinical worsening), while secondary endpoints (symptomatic severity) will be examined using appropriate (descriptive, Area Under the Curve (AUC), and trajectory) comparisons.

Sharing of de-identified data from this study will be critical because it will help characterize this patient population and, if positive results, would immediately lead to a potential new treatment for COVID-19. Therefore it is planned that a pre-print of the article along with de-identified data will be posted on a public repository such as arxiv (arxiv.org). This has been standard during the pandemic in order to share results as rapidly as possible.

Additional measurements:

Baseline: vital signs (pulse, blood pressure, temperature), O2 saturation, weight and height, symptoms and symptomatic severity.

Follow-up: daily vital signs, O2 saturation, adverse events (participant self-report).

Risks

Potential risks associated with study assessments

There are no risks associated with any of the assessments.

Potential risks associated with study medication

Fluvoxamine:

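### No covariate is named for the primary survival analysis, although pre-dose O2 saturation is measured in everyone and a fall in saturation is part of the endpoint; adjusting for it would add some power and correct chance imbalance

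*Combined protocol and SAP*

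**What the plan says.** Under Data management and analysis, the plan states: "The primary analysis will be survival analysis of the primary outcome (clinical worsening"). Outcome Assessments adds that the endpoint is analysed as time to worsening, in everyone confirmed to have taken at least one dose. No test, model or covariate list appears, and because the document is both protocol and SAP, it refers to no later text that would supply one.

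The definition of clinical worsening has two parts, and both must be met. The first is dyspnea and/or hospitalization for shortness of breath or pneumonia. The second is saturation below 92% on room air and/or "supplemental oxygen requirement in order to keep O₂ saturation" above 92%.

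Saturation is a baseline measurement (Additional measurements): "Baseline: vital signs (pulse, blood pressure, temperature), O2 saturation, weight and height, symptoms and symptomatic severity". Study Procedures places a reading before the first dose, as part of "confirming medical stability via oxygen saturation monitor, and vital sign measurement".

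Study Design anticipates stratifying by four age bands and sex and leaves the final choice to the biostatistician. Saturation is not mentioned there. The power analysis mentions possible gains from stratification and from Kaplan-Meier methods, but none from baseline adjustment.

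**The concern.** Starting saturation is on the same scale as part of the endpoint. A participant who starts at 93% has less far to fall than one who starts at 98%, so the reading is a natural prognostic variable. The exclusion criteria remove people who already meet the full endpoint, which also requires dyspnea or hospitalization. No saturation floor is stated, so readings near the threshold are possible at entry.

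The anticipated strata do not balance this variable. Stratifying on it also looks impractical, because the monitor is sent together with the study medication. That leaves the analysis as the workable place to use it. If the analysis does not, some power is lost on average. In a trial that happens to be imbalanced, there is no prespecified way to separate the imbalance from the drug effect. Leaving the choice open until coded results exist would also weaken any adjusted result reported later.

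**Working it through.** **1. The plan's own figure.** The inputs, from the power analysis, are: "It assumes 80% power, alpha=0.05, and a 20% rate of progression to serious symptoms in the placebo group"; 5% on fluvoxamine; and 76 per group. Sidedness is not stated; two-sided reproduces the table. With pooled variance and no continuity correction,

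n = [1.960·√(2·p̄(1−p̄)) + 0.8416·√(p₁(1−p₁)+p₂(1−p₂))]² / (p₁−p₂)²

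With p₁ = 0.20, p₂ = 0.05 and p̄ = 0.125: (1.960×0.4677 + 0.8416×0.4555)² / 0.0225 = 1.690/0.0225 = 75.1, rounded up to 76. The same formula gives 90, 108, 131, 160 and 199 for the other rows, so the whole table reproduces. Power at 76 per group is 80.5% for 20% vs 5% and 57% for 20% vs 8%.

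**2. Events.** 76×0.20 + 76×0.05 = 15.2 + 3.8 = 19. The implied hazard ratio is ln(0.95)/ln(0.80) = 0.23.

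**3. Chance imbalance.** The documents give no SD for saturation; 1.5 points is assumed. The SE of the difference in means is 1.5×√(2/76) = 0.243 points. A gap above 0.4 points is 0.4/0.243 = 1.64 SE, so it occurs in about 10% of trials, or about 5% in each direction. A half-point gap is 2.05 SE, about 4% in both directions together.

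**4. Simulated power.** Assumptions: 76 per arm; integer saturation with mean 96.5 and SD 1.5, truncated at 92; exponential event times over 15 days, calibrated to the stated risks; 3,000 trials per setting. The unadjusted log-rank test is compared with the likelihood-ratio test from a Cox model with treatment and saturation.

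| Assumed HR per point lower | 20% vs 5%: log-rank / adjusted | 20% vs 8%: log-rank / adjusted |
|---|---|---|
| 1.3 | 83% / 85% | 58% / 60% |
| 1.5 | 82% / 84% | 57% / 60% |
| 1.8 | 83% / 88% | 60% / 66% |

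The simulation error of one power figure is about √(0.83×0.17/3000) = 0.7 points. An independent repeat with 2,500 trials per cell gave 82-84% against 85-88%, and 57-59% against 60-64%.

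**5. How much comes from the covariate.** The table changes the test as well as the model. A further run at 20% vs 5% gave, for log-rank / unadjusted likelihood ratio / adjusted likelihood ratio, 83.3/84.0/84.8, 82.7/83.3/85.0 and 83.6/84.5/88.1. By subtraction the change of test accounts for 0.6 to 0.9 points, and the covariate for 0.8, 1.7 and 3.6 points.

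**6. Trials with an imbalance of 0.4 to 0.7 points.** For HR 1.3, 1.5 and 1.8 per point:
- Imbalance against the drug, true 20% vs 5%: power 76%, 70%, 66% unadjusted; 85%, 85%, 87% adjusted.
- Imbalance favouring the drug, no true effect: false significant benefit 4.8%, 7.6%, 9.0% unadjusted; 2.7-2.8% adjusted (nominal 2.5%).

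**7. A wider range.** With a standard-normal covariate and a hazard ratio per SD of 1.0 to 4.48, the gain runs from about 0 to 11 points at 20% vs 5% and from about 0 to 18 at 20% vs 8%. For comparison, 1.3 and 1.8 per point correspond to 1.3^1.5 = 1.48 and 1.8^1.5 = 2.41 per SD.

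**8. Type I error over all randomizations.** Unadjusted: 5.0-5.7%. Adjusted: 4.8-6.0% across all runs. The simulation error at 2,000 trials is about 0.5 points.

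**The case against.** The strongest reply is that the plan does not specify an unadjusted analysis. A reader might infer one from the missing covariate list, but the text is silent: it says survival analysis and no more. The remark on power gained by stratification even suggests that the strata were meant to enter the analysis. This stands. The point is that a useful covariate is not named, not that it is expressly left out.

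A reader might also infer that an imbalance could create or hide the planned effect, or that the unadjusted test is invalid. The figures do not support either. A half-point imbalance multiplies the hazard ratio by 1.3^0.5 = 1.14, 1.5^0.5 = 1.22 or 1.8^0.5 = 1.34, against a planned value of 0.23. Type I error over all randomizations stays near 5%, and average unadjusted power is above the 80% target at 20% vs 5%.

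Three further objections stand in part. The size rests on an assumed mean, SD, truncation and prognostic strength. The data were generated from the same model that was then fitted, which favours adjustment. And low saturation alone is not the endpoint, since dyspnea or hospitalization is also required. These limit confidence in the size, but they do not remove the direction of the benefit or its low cost.

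**Conclusion.** The concern holds in a limited form. Pre-dose saturation is collected, precedes treatment and lies on the scale of one endpoint component, yet no text uses it in the primary analysis. An unadjusted log-rank test would be valid and adequate at the planned effect. Under the assumed SD of 1.5 points and hazard ratio of 1.3 to 1.8 per point, adjustment adds about 1 to 5 points of power at 20% vs 5%, of which up to 1 point comes from the change of test, and about 2 to 6 points at 20% vs 8%. If saturation is only weakly prognostic, the average gain is negligible.

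The larger benefit is conditional. In about one trial in 20, an imbalance above 0.4 points against the drug lowers unadjusted power to about 66-76%, where the adjusted test keeps 85-87%. Confidence is high for the omission and the direction, and moderate for the size. This is a worthwhile improvement, not a flaw that invalidates the design.

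**What to change.** Before the coded two-group analysis is run, state the primary analysis as a Cox model for time to clinical worsening with treatment and continuous pre-dose O2 saturation. Account for the randomization factors in a sparse form, for example age as one continuous term plus sex. Test treatment by likelihood ratio, which stays finite if an arm has no events. Give the hazard ratio with a profile-likelihood or Firth interval in case an arm has very few events. Report Kaplan-Meier curves and the unadjusted log-rank test as supporting results.

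The cost is a few sentences and no new data. The hazard ratio becomes conditional on the covariates, and there are fewer events per parameter: 19/2 = 9.5 with treatment and saturation alone, and 19/4 = 4.75, about 5, with age and sex added. The simulations above did not include age and sex, so the list should not grow beyond these terms.

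### No baseline adjustment is specified for the symptom-severity AUC and trajectory comparisons, although baseline severity is collected; naming it as a covariate is a free gain in precision for this secondary endpoint.

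*Combined protocol and SAP*

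**What the plan says.** The endpoint is item 3 of the secondary endpoints under Outcome Assessments: "Total symptomatic severity during the 15 days using a continuous scale" from 0 to 10, with "symptomatic data collected approximately twice daily via the technique of Ecological Momentary Assessment". The same item says: "The most severe symptom at baseline will be the focus".

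The whole of its planned analysis is one clause under Data management and analysis: "secondary endpoints (symptomatic severity) will be examined using appropriate (descriptive, Area Under the Curve (AUC), and trajectory) comparisons".

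Additional measurements lists what is recorded at the start: "Baseline: vital signs (pulse, blood pressure, temperature), O2 saturation, weight and height, symptoms and symptomatic severity". The only use the plan gives to baseline severity is to choose which symptom is followed.

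Study Design sets 1:1 allocation, stratified by age (four anticipated bands) and sex. Baseline symptom severity is not a stratification factor.

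**The concern.** The outcome is the course of a 0-10 rating, and the rating of the same symptom at entry is an obvious candidate predictor of that course. Eligibility requires one or more of nine quite different symptoms and sets no minimum severity. Participants may therefore enter with different symptoms at different starting scores. If the AUC is compared between arms without the starting score, the between-patient variation that the score explains stays in the error term.

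Neither the design nor the stated analysis deals with this. Stratification does not balance severity, and no covariate is named.

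Two things are at stake, both confined to this endpoint. One is precision that the trial could have from data it already holds. The other is credibility: if the model is chosen after the data can be compared by arm, the choice between adjusted and unadjusted results, or between AUC and trajectory, is open to question. Analysing the arms under coded labels does not remove this, because the difference between them is still visible.

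**Working it through.** **The plan's own figure.** The only sample-size calculation is for the primary endpoint (Power analysis): "It assumes 80% power, alpha=0.05, and a 20% rate of progression to serious symptoms in the placebo group". The two-sided, uncorrected two-proportion formula is

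n per group = [1.96·√(2·p̄·(1−p̄)) + 0.8416·√(p1(1−p1) + p2(1−p2))]² / (p1−p2)².

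With p1 = 0.20, p2 = 0.05 and p̄ = 0.125, this is [1.96·√0.21875 + 0.8416·√0.2075]² / 0.0225 = (0.9167 + 0.3834)² / 0.0225 = 75.1, so 76. The other five rows (90, 108, 131, 160, 199) also reproduce exactly. The table says nothing about symptom severity, so there is no stated figure for the AUC to test.

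**Inputs for the AUC.**
- 76 per arm, alpha 0.05 and 80% power are taken from Power analysis; two-sided testing is inferred from the table.
- The SD of the AUC and its correlation r with baseline severity are not in the documents. Differences are therefore expressed in SD units, and r is assumed over 0.2 to 0.7.

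**Unadjusted comparison.** Detectable difference = (1.96 + 0.8416)·√(2/76) = 2.8016 × 0.1622 = 0.454 SD.

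**With baseline severity as covariate.** The residual variance is multiplied by 1 − r². The detectable difference becomes 0.454·√(1 − r²). Power at a true difference of 0.454 SD is Φ(2.8016/√(1 − r²) − 1.96). The equivalent total sample size is 152/(1 − r²).

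| Assumed r | Variance cut | Detectable difference (SD) | Power at 0.454 SD | Equivalent total n |
|---|---|---|---|---|
| none (unadjusted) | – | 0.454 | 80.0% | 152 |
| 0.2 | 4% | 0.445 | 81.6% | 158 |
| 0.3 | 9% | 0.434 | 83.6% | 167 |
| 0.5 | 25% | 0.394 | 89.9% | 203 |
| 0.7 | 49% | 0.325 | 97.5% | 298 |

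A simulation of 4,000 trials for each of r = 0.3, 0.5 and 0.7 gave adjusted power of 83.3%, 89.2% and 97.1%. The unadjusted test gave 79.5%, 79.7% and 78.9%.

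**Cost of estimating the covariate.** With N = 152 and one covariate, the expected variance factor is (1 − r²)(1 + 1/(N − 4)) = (1 − r²)(1 + 1/148). It equals 1 when r² = 1/149, that is r ≈ 0.08. Above that, adjustment for baseline severity gains.

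Four age bands and sex add four parameters. If they predicted nothing and were not balanced by design, the factor for all five would be 1 + 5/(152 − 5 − 3) = 1.035. At r = 0.2 the product is 0.96 × 1.035 = 0.99, which is no loss but almost no gain. Stratification keeps age and sex close to balanced, so the real cost should be smaller.

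**The case against.** The strongest reply is that the plan does not say the comparison is unadjusted. It promises appropriate comparisons, which leaves ANCOVA open. It also lists trajectory comparisons, which may already use the baseline value as a first time point or intercept. This stands. A reader might infer that the sponsor has decided against adjustment, or left it out because the endpoint is secondary. The documents record neither a decision nor a reason. What they show is that no adjustment is specified.

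Three further points on the other side are fair:

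- **Validity.** A reader might infer that an unadjusted AUC comparison is biased by chance differences in baseline severity. Under 1:1 randomisation it is unbiased, and its standard error and type I error already allow for such differences. The issue is efficiency.
- **The plan's claim about precision.** The plan says its technique "should greatly increase precision and power". A reader might infer that omitting the covariate undoes that gain. It does not: the plan credits frequent measurement of the patient's most relevant symptom, and adjustment would be a separate gain.
- **Size.** The correlation may be low. Following each participant's worst symptom on a 0-10 scale may narrow the range of starting scores. The Background also describes an illness that often deteriorates in the second week, so the entry score may predict the 15-day course poorly. At r = 0.2 the gain is under two percentage points of power. The absence of a severity floor at entry works the other way, but the documents do not settle it.

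None of this is a reason to leave the model unstated. The data are collected in any case, and the gain from adjustment is most credible when the covariates are fixed in advance.

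**Conclusion.** The point holds as a free improvement to a secondary endpoint. The plan intends AUC and trajectory comparisons of symptom severity and specifies no baseline adjustment, although it collects baseline severity and stratifies by age and sex. If the comparison is left unadjusted, it will be valid but less precise than the data allow.

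The size rests entirely on an assumed correlation. The gain ranges from slight (r = 0.2: 4% less variance, about 82% power in place of 80%) to substantial (r = 0.7: 49% less variance, about 97% power). The figures also assume 76 analysed per arm, a roughly linear relation between baseline severity and AUC, and two-sided alpha of 0.05. The documents do not support a firm statement that much precision is being lost. They do support the statement that an easy means of gaining some has not been written down. The primary time-to-worsening analysis and the sample size of 152 are unaffected.

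**What to change.** Before unblinding, and preferably before any comparison of symptom data by coded arm, add to Data management and analysis:

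- The 15-day AUC of the tracked symptom will be analysed by ANCOVA with terms for arm, baseline severity of that symptom, age group (as finally used for stratification) and sex.
- The trajectory model will account for baseline severity, with a statement of how it enters.
- The adjusted AUC difference, with its confidence interval, will be the main result for this endpoint. An unadjusted difference may be shown alongside it as supportive.

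The cost is a few lines of analysis-plan wording. No new data, contacts or participants are needed.

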- 5) Able to provide informed consent.

Exclusion criteria:

- 1) Illness severe enough to require hospitalization or already meeting study's primary endpoint for clinical worsening.
- 2) Unstable medical comorbidities including, but not limited to: Severe underlying lung disease (COPD on home oxygen, interstitial lung disease, pulmonary hypertension), decompensated cirrhosis, Congestive heart failure (stage 3 or 4 per patient report and/or medical records).
- 3) Immunocompromised (solid organ transplant, BMT, AIDS, on biologics and/or high dose steroids (>20mg prednisone per day))
- 4) Already enrolled in another COVID 19 clinical trial
- 5) Unable to provide informed consent (eg moderate-severe dementia diagnosis)
- 6) Unable to perform the study procedures

Rationale for inclusion & Exclusion Criteria: Adults 18 and older who are not already medically compromised (eg severe lung disease) are at risk for developing clinical deterioration late in their clinical course. The Inclusion criteria will ensure that we collect as generalizable sample as possible of at-risk adults, while the exclusion criteria will ensure that we do not recruit individuals who are likely to need immediate hospitalization or are otherwise too medically unstable to participate in an outpatient study with remote monitoring. Older adults will be included; exclusion criteria will exclude individuals who are highly frail, medically compromised, or highly cognitively impaired.

Study Procedures, Materials, and Potential Risks

Sources of Materials

Research materials will be obtained by remote interviews, self-reports, medical records (when available), and remote self-monitoring. All materials will be obtained solely for the purposes of the research study. All data collected from the participants enrolled in the study will be stored and maintained confidentially and no identifying information, such as participant names, will be disclosed in any published documents.

Study Procedures

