All enrolled participants will also be sent a longterm follow up survey which asks about persistent COVID 19 symptoms, and a PROMIS scale which asks about functioning and quality of life.

Management: To protect research staff, there will be no face-to-face contact with participants; all interactions will be fully-remote via Zoom videoconference and/or phone/text/email, as well as REDCap surveys pushed out to patients via their smartphones or other devices.

For consented participants who start protocolized treatment we will inform their relevant medical providers, such as a PCP, towards the goal of an informed and collaborative management strategy.

As this is a “prevention of clinical deterioration” study, it is anticipated that a minority (~10-15%) of participants will become hospitalized during the study, and that this will most likely occur during the randomized phase. Research staff under the physician investigators’ supervision will provide support including engagement with participants’ caregivers and physicians to ensure timely medical contact and emergency care (including calling 911).

If a study participant develops a decrease in oxygen saturation to less than 90% on room air on >2 readings, persistent increase in respiratory rate to >30 breaths per minute, persistent increase in Heart Rate to > 120 beats per minute, alteration in mentation, or severe worsening in shortness of breath, the research staff will direct them to seek emergency medical care at the nearest emergency department. If none of the above conditions are met, but the research staff still feel that the participant is unwell, one of the physician investigators will evaluate the participant via phone/telehealth and direct them for further care if needed. When a participant is directed to seek emergency medical care, they will be instructed to use a mask if available, and to identify themselves to EMS or to the Emergency Department staff as having been diagnosed with COVID-19.

Safety Assessments

We will assess for adverse events (including serious adverse events) daily via participant self-report during the first 15 days, and then again at the end of the study.

Outcome Assessments

As this is a prevention (of clinical deterioration) trial, the primary endpoint will be a “time to” clinical worsening analysis. Following the intention to treat principle, all participants who are confirmed to have taken at least one dose of study medication are included in the analyses.

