General comments: Fluvoxamine is an antidepressant drug that functions as a selective serotonin reuptake inhibitor (e.g., similar to escitalopram (Lexapro), fluoxetine (Prozac), sertraline (Zoloft), etc – among the most commonly prescribed drugs in the US). Its risk profile below is for chronic use in a psychiatrically ill population; the risks for short-term use in a non-psychiatric population are likely lower. The research team will carefully evaluate co-prescribed drugs as well as OTC medications and caffeine use, to mitigate drug-drug interactions. We anticipate approximately 20% of participants will be on current SSRI/SNRI use at recruitment – will include these individuals, so long as the participant can be safely switched over to fluvoxamine briefly.

Likely risks: none.

Less likely (1-10%): Nausea, Vomiting, Weight loss, Yawning, Loss of appetite, Agitation/Nervousness/Anxiety, Insomnia, Somnolence, Tremor, Headache, Dizziness, Palpitations, Tachycardia (high heart rate), Abdominal pain, Dyspepsia (indigestion), Diarrhea, Constipation, Hyperhidrosis (excess sweating), Asthenia (weakness), Malaise, Sexual dysfunction (including delayed ejaculation, erectile dysfunction, decreased libido, etc.), Xerostomia (dry mouth).

Rare (<1%): Arthralgia, Hallucination, Confusional state Extrapyrmidal side effects (e.g. dystonia, parkinsonism, tremor, etc.), Orthostatic hypotension, Cutaneous hypersensitivity reactions (e.g. oedema [buildup of fluid in the tissues], rash, pruritus), Mania (elevated mood together with reduced need for sleep and increased energy), seizures, Abnormal hepatic (liver) function, Photosensitivity (being abnormally sensitive to light), Galactorrhoea (expulsion of breast milk unrelated to pregnancy or breastfeeding).

Potential risk associated with Breach of Confidentiality:

One risk of participating in this study is that confidential information may be accidentally disclosed. We will use our best efforts to keep the information about participants secure. All private information is stored in secured areas and on encrypted and password-protected servers.

Other risks:

There may also be unknown risks. We will adjust the informed consent process if new risks are identified.

Adequacy of Protection Against Risks

Recruitment and Informed Consent

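### Participant self-report is the only source named for adverse events, including serious ones, so non-respiratory serious events can be missed in participants who cannot report

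*Combined protocol and SAP*

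**What the plan says.** All references are to the combined protocol and SAP.

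- **Safety Assessments:** "We will assess for adverse events (including serious adverse events) daily via participant self-report during the first 15 days". One further assessment takes place when the study ends, and it has no source of its own.
- **Additional measurements:** "Follow-up: daily vital signs, O2 saturation, adverse events (participant self-report"). No second source is given.
- **Outcome Assessments, after secondary endpoints 1 and 2** (the deterioration scale, which runs up to ventilation and death, and the day counts for oxygen, hospitalization and ventilation): "They will be collected in retrospect via patient or family report and/or medical records".
- **Sources of Materials**, for research data in general: "Research materials will be obtained by remote interviews, self-reports, medical records (when available), and remote self-monitoring". Adverse events are not mentioned there.
- **Study Design**, after the randomized phase: "all participants will be followed for approximately 30 days to collect clinical data (i.e., on hospitalization and other clinical outcomes"). No source is named.
- **Management:** staff deal with caregivers and physicians so that participants get timely care. This is not described as a way of collecting adverse events.
- **Potential risks associated with study medication:** the rare effects (under 1%) include "Hallucination, Confusional state", seizures and abnormal liver function.

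**The concern.** The plan expects some participants to become unable to report. Its deterioration scale has levels for ventilation and death, and Management lists altered mentation as a trigger for emergency referral. A participant who dies cannot give a final report. A survivor who was sedated or confused may not remember the period asked about. Some effects are not apparent to the participant at all: a liver abnormality may show only in hospital results, and the plan schedules no laboratory tests of its own.

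For its deterioration outcomes the plan turns to family and records, but it does not extend those sources to safety. Reporting ability will be related to deterioration, and deterioration is what the drug is meant to change. The completeness of the safety data may therefore differ between arms. The trial's stated aim is a drug that can be given widely to outpatients with mild illness, so serious events in those who become sick are part of the evidence it has to supply.

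**Working it through.** **Reading the sections together.** Two sections state how adverse events are collected, and both name the participant. None names a relative, a record or a treating clinician for this purpose. The plan therefore has two routes:

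| Event | Source named in the plan |
|---|---|
| Death, ventilation, dyspnea-related hospitalization, oxygen need | Patient, family, records (as efficacy outcomes) |
| Any other serious event | Participant |
| Onset of an event and its relation to drug | Participant, so far as any source is named |

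**The plan's own sample size.** With 20% vs 5%, two-sided alpha 0.05, 80% power, pooled variance and no continuity correction:

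n = [1.960 × √(2 × 0.125 × 0.875) + 0.842 × √(0.20 × 0.80 + 0.05 × 0.95)]² / 0.15² = 75.1, rounded up to 76 per group, as stated.

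The other five rows of the table reproduce as well. The present point does not depend on this figure; it only borrows the 20%, 5% and 76.

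**Who is affected.**
- Expected to deteriorate: 76 × 0.20 = 15.2 on placebo and 76 × 0.05 = 3.8 on fluvoxamine.
- Expected to be hospitalized (Management, 10–15%): 152 × 0.10 = 15.2 to 152 × 0.15 = 22.8, so 15 to 23 participants.
- The documents give no rate for ventilation, confusion, death or serious adverse events, so the number unable to report cannot be derived.

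**Illustration with assumed rates.** Assume that serious events not otherwise captured occur in 30% of those who deteriorate and 5% of the rest. Let f be the fraction of those who deteriorate whose events are never reported.

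- True placebo count: 15.2 × 0.30 + 60.8 × 0.05 = 4.56 + 3.04 = 7.60.
- True fluvoxamine count: 3.8 × 0.30 + 72.2 × 0.05 = 1.14 + 3.61 = 4.75.
- True difference: 2.85.
- Recorded counts: 7.60 − 4.56f and 4.75 − 1.14f.
- Loss of difference: (4.56 − 1.14)f = 3.42f. As a share: 3.42f / 2.85 = 1.2f.

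| f (assumed) | Placebo recorded | Fluvoxamine recorded | Difference | Shrinkage |
|---|---|---|---|---|
| 0.05 | 7.37 | 4.69 | 2.68 | 6% |
| 0.10 | 7.14 | 4.64 | 2.51 | 12% |
| 0.25 | 6.46 | 4.47 | 2.00 | 30% |
| 0.50 | 5.32 | 4.18 | 1.14 | 60% |

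**Sensitivity to the assumed event rates.** In this model the shrinkage is f × a / (a − b), where a is the rate in those who deteriorate and b the rate in the rest. With b = 5% and a between 20% and 40%, the multiplier runs from 0.20/0.15 = 1.33 to 0.40/0.35 = 1.14. At f = 0.50 the shrinkage is then 67% to 57%, and at f = 0.25 it is 33% to 29%. The fraction unable to report matters far more than the event rate.

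**Direction.** Placebo loses 4.56f events and fluvoxamine 1.14f, four times as many on placebo. Placebo then looks safer than it is, and the bias runs against fluvoxamine.

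**The case against.** The other side has four arguments of substance.

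1. **Records are not excluded.** Sources of Materials allows medical records for research data in general, and the follow-up in Study Design covers hospitalization and other clinical outcomes. In Safety Assessments, the mention of self-report is attached to the daily assessments; that it also governs the end-of-study assessment is a plausible reading, not stated text. All this stands. It means that self-report is the only source named for adverse events, not that other sources are barred. A general permission still does not tell staff to look in the records for serious events.

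2. **The gravest events are captured.** A reader might infer that deaths and ventilations would go unrecorded. The documents do not support that: both are levels of the deterioration scale, which draws on family and records. The gap is limited to other serious events and to timing and drug-relatedness.

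3. **Most who deteriorate can still report.** The primary endpoint can be met with dyspnea and saturation below 92% on room air, without admission. Such a participant can usually answer a survey, a transient episode can be reported on a later day, and survivors are asked again at the end. This stands as a reason to doubt values of f near one half. It does not help those who die, stop reporting or do not recall.

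4. **Few drug-related events are at risk.** The rare effects are listed at under 1%, which is fewer than 76 × 0.01 = 0.76 expected per effect in the active arm. Nor does Data management and analysis specify a formal comparison of serious events. Both are correct. The comparison meant here is any tabulation of events by arm, and in a trial of this size one unrecorded drug-related serious event would matter.

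**Conclusion.** The point holds in a limited form. As written, the plan names only participant self-report for adverse events, including serious ones. Serious events other than death, ventilation and dyspnea-related hospitalization, and the onset and drug-relatedness of events, can be missed in participants who are incapacitated, die or stop reporting.

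Two stronger inferences should be resisted. The first is that the gap would flatter fluvoxamine. If the drug prevents deterioration, the lost events fall mainly on placebo and the comparison is biased against it, although drug-related events in hospitalized participants could still go unrecorded. The second is that a large share of the safety contrast would certainly be lost. The 60% figure requires that half of those who deteriorate never report; at one in ten it is 12%. These percentages rest on assumed rates and on the plan's 20% and 5% deterioration rates. What rests on the text is the mechanism: incomplete recording that follows deterioration and so can differ by arm. If the arms deteriorate equally, the model predicts equal losses, but events are still lost.

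This is a cheap improvement. It does not affect the primary endpoint or the sample size.

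**What to change.** In Safety Assessments and in Additional measurements, add that serious adverse events are also obtained from family members or medical records for any participant who is hospitalized, dies or stops reporting. Have blinded staff collect event type, onset date and information on relation to study drug, in the same way in both arms, through the contact and records request already planned for secondary endpoints 1 and 2. Keep self-report for non-serious events.

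The cost is one sentence in each place, a few more items on a form, and slightly longer abstraction for the 15 to 23 participants expected to be hospitalized, plus any others who die or stop reporting.
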